# **Informed Consent/Assent**

10. The participant (or legally acceptable representative) has provided documented informed consent/assent for the study.

See Section 10.7, Appendix 7 for country-specific inclusion criteria requirements.

# 5.2 Exclusion Criteria

The participant must be excluded from the study if the participant:

#### **Medical Conditions**

- 1. Has chronic (≥30 days' duration) IA, relapsed/recurrent IA, or refractory IA that has not responded to prior antifungal treatment.
- 2. Has cystic fibrosis, pulmonary sarcoidosis, aspergilloma, or allergic bronchopulmonary aspergillosis.
- 3. Has known hypersensitivity or other serious adverse reaction to any azole antifungal therapy, or to any other ingredient of the study treatment used.

- 4. Has any known history of torsade de pointes, unstable cardiac arrhythmia or proarrhythmic conditions, a history of recent myocardial infarction, congenital or acquired QT prolongation, or cardiomyopathy in the context of cardiac failure within 90 days of time of first dose of study treatment.
- 5. Has known hereditary fructose intolerance.
- 6. Has known galactose intolerance, Lapp lactase deficiency, or glucose-galactose malabsorption.
- 7. Is on artificial ventilation at the time of first dose of study treatment.
- 8. Has any condition that, in the opinion of the investigator, may interfere with optimal participation in the study.

## **Prior/Concomitant Therapy**

9. Has received any treatment specifically listed in Table 2 within the specified timeframes before the start of study treatment.

Prohibited Medications Before Start of Study Treatment	Prohibited Time Period Before Day 1 of Study Treatment a
Any investigational drug (new chemical or biological entities): may be permitted with the approval of the Sponsor's Clinical Director	Only permitted with approval of the Sponsor's Clinical Director prior to start of study therapy
Systemic antifungal treatment (oral, intravenous, or inhaled) when used to treat current fungal infection episode	Prohibited if duration of treatment for current fungal infection is ≥96 hours before Day 1
Azole antifungal prophylaxis with mold activity (ie, itraconazole, voriconazole, isavuconazole)	Prohibited unless approval provided by the study Sponsor's Clinical Director prior to study randomization. Without Sponsor approval, prohibited if duration of mold-active azole prophylaxis therapy exceeds 13 days prior to study randomization
Astemizole	Prohibited if taken within 24 hours before Day 1
Cisapride, ebastine, halofantrine, pimozide, quinidine, and terfenadine	Prohibited if taken within 24 hours before Day 1
Ergot alkaloids (ergotamine, dihydroergotamine, or other members of this class)	Prohibited if taken within 24 hours before Day 1

#### Table 2 Prohibited Medications Before Start of Study Treatment

Prohibited Medications Before Start of Study Treatment	Prohibited Time Period Before Day 1 of Study Treatment a
Disopyramide	Prohibited if taken within 24 hours before Day 1
Bepridil	Prohibited if taken within 24 hours before Day 1
Ibutilide	Prohibited if taken within 24 hours before Day 1
Haloperidol	Prohibited if taken within 24 hours before Day 1
HMG-CoA reductase inhibitors metabolized via CYP3A4 (eg, simvastatin, lovastatin, and atorvastatin)	Prohibited if taken within 24 hours before Day 1
Atazanavir, efavirenz, fosamprenavir, or ritonavir	Prohibited if taken within 24 hours before Day 1
Venetoclax	Prohibited if taken within 24 hours of Day 1

Abbreviations: CYP = cytochrome P450; HMG-CoA=beta-hydroxy-beta-methylglutaryl-CoA.

a These waiting times should be observed immediately before start of study treatment and during study treatment in participants receiving a prohibited treatment as prior treatment.

#### **Prior/Concurrent Clinical Study Experience**

10. Has enrolled previously in the current study and been discontinued.

#### **Diagnostic Assessments**

- 11. Has QTc prolongation (based on either Fridericia or Bazett's correction) at screening >500 msec.
- 12. Has significant liver dysfunction (defined as total bilirubin  $>1.5 \times$  ULN AND AST or ALT  $>3 \times$  ULN with normal alkaline phosphatase) at screening.

13. Has calculated creatinine clearance <20 mL/min/1.73 m^2 (modified Schwartz formula) at screening. Creatinine clearance will be calculated using the following equation:

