• If during study treatment the participant has AST or ALT ≥3 × ULN and bilirubin ≥2 × ULN and alkaline phosphatase <2 × ULN, then study therapy may be interrupted for up to 3 days with repeat monitoring of liver function testing. Study therapy may be resumed if repeated liver function testing parameters no longer meet the criteria outlined above and the change is unrelated to study intervention based on the opinion of the investigator. Study therapy should be permanently discontinued if liver function testing continues to exceed the specified parameters with repeat testing regardless of relationship to study medication.

For participants who are discontinued from study intervention but continue to be monitored in the study, all visits and procedures, as outlined in the SoA, should be completed.

See Section 10.7, Appendix 7 for country-specific discontinuation of study intervention requirements.

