# 8.4.7 Events of Clinical Interest (ECIs)

Selected nonserious and SAEs are also known as ECIs and must be reported to the Sponsor.

Events of clinical interest for this study include:

1. An elevated AST or ALT lab value that is greater than or equal to 3X the upper limit of normal and an elevated total bilirubin lab value that is greater than or equal to 2X the upper limit of normal and, at the same time, an alkaline phosphatase lab value that is less than 2X the upper limit of normal, as determined by way of protocol-specified laboratory testing or unscheduled laboratory testing.\*

\*Note: This section reflects the handling of nonserious ECI. ECI events meeting SAE criteria are to be reported in the same manner as SAE. The purpose of the criteria is to specify a threshold of abnormal hepatic tests that may require an additional evaluation for an underlying etiology. The study site guidance for assessment and follow-up of these criteria can be found in the Investigator Study File Binder (or equivalent).

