# 8.9.1 Screening

All screening procedures outlined in the SoA must be performed within 14 days before enrollment into the study. Informed consent/assent must be obtained from the participant or legally acceptable representative of each participant before any study-specific procedures are performed other than those procedures conducted for the purpose of routine clinical care. Assent will be obtained from minors according to institutional practices. Before treatment assignment, potential participants must be evaluated to determine whether they fulfill the entry requirements as set forth in Sections 5.1 and 5.2. Local laboratory tests (pregnancy, hematology/chemistry, imaging, and mycology testing) will be used to evaluate eligibility criteria. Only potential participants with clinically acceptable results from all screening criteria are to be enrolled in the study.

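### A child can pass the liver exclusion with laboratory values that already meet the on-treatment interruption and ECI limits, because the alkaline phosphatase conditions differ

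*Combined protocol and SAP*

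**What the plan says.** **Entry.** Section 5.2, criterion 12, defines significant liver dysfunction by three conditions that must hold together: total bilirubin above 1.5 x ULN, AST or ALT above 3 x ULN, and both of these "with normal alkaline phosphatase) at screening". The protocol does not say what counts as normal. No other eligibility criterion sets a numeric liver limit, and Appendix 7 does not change this one for any country.

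**On treatment.** Section 7.1 acts on "AST or ALT ≥3 × ULN and bilirubin ≥2 × ULN and alkaline phosphatase <2 × ULN". Therapy may then be interrupted for up to 3 days. It may resume if repeat values no longer meet the limits and the investigator judges the change unrelated to study treatment. Otherwise, "Study therapy should be permanently discontinued if liver function testing continues to exceed the specified parameters with repeat testing", whatever the cause.

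**Reporting.** Section 8.4.7 defines the one named event of clinical interest by the same transaminase and bilirubin limits together with "an alkaline phosphatase lab value that is less than 2X the upper limit of normal". It makes no exception for values present before dosing. Table 7 (Section 8.4.1) requires potential drug-induced liver injury arising after allocation to be reported within 24 hours.

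**Judgment clauses.** Criterion 8 excludes a child who "Has any condition that, in the opinion of the investigator, may interfere with optimal participation in the study". Section 8.9.1 adds: "Only potential participants with clinically acceptable results from all screening criteria are to be enrolled in the study".

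**The concern.** An entry rule and a stopping rule need not share thresholds, but they should not leave a region where a child is admitted with values that the protocol treats, days later, as grounds for interruption and expedited reporting. Here an ALP modestly above normal switches the exclusion off altogether, however high bilirubin and transaminases are, and does not switch off the on-treatment rules.

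Three things are at stake.

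- **Safety.** Hepatic toxicity is an identified risk of the drug (Section 2.3), and the child is dosed with both markers already raised.
- **Interpretation.** A pre-existing abnormality can be reported as potential drug-induced liver injury and can end treatment.
- **Information.** Participants who discontinue are not replaced (Section 5.5). A child stopped before 7 days of IV treatment falls outside the PK population (Section 9.5.2). Without at least 7 days of oral therapy, the child also does not count toward the target of at least 15 in Section 4.1.

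**Working it through.** The plan has no figure to reproduce, so the check is a comparison of conditions, all in multiples of ULN. *Normal* ALP is read as not above 1 x ULN.

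| Condition | Criterion 12 (Section 5.2) | Sections 7.1 and 8.4.7 |
|---|---|---|
| Bilirubin | > 1.5 | ≥ 2 |
| AST or ALT | > 3 | ≥ 3 |
| ALP | ≤ 1 (normal) | < 2 |
| When applied | screening | 7.1: during treatment; 8.4.7: protocol-specified or unscheduled tests |

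**Step 1: test cases.**

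| Bilirubin | ALT | ALP | Excluded by criterion 12? | Meets 7.1 and 8.4.7 limits? |
|---|---|---|---|---|
| 2.5 | 5 | 0.9 or 1.0 | yes | yes |
| 2.5 | 5 | 1.2, 1.5 or 1.9 | **no** | **yes** |
| 2.5 | 5 | 2.0 | no | no |
| 1.8 | 5 | 0.9 | yes | no |
| 2.0 | 3.0 | 0.9 | **no** | **yes** |

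**Step 2: the gap.** A value set is in the gap if it meets the on-treatment limits and is not excluded. That gives 1 < ALP < 2 with bilirubin ≥ 2 and AST or ALT ≥ 3. The last row shows a second gap, on the boundary only: at AST or ALT of exactly 3.0 with bilirubin ≥ 2, the on-treatment limits are met even with normal ALP, because one rule uses > and the other ≥. A grid in steps of 0.1 (bilirubin 0.5 to 6.0, AST/ALT 0.5 to 10.0, ALP 0.3 to 3.0) found no other mismatch of this kind. The grid shows that the gap exists. It does not estimate how often children fall in it.

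**Step 3: the other direction.** With normal ALP and AST or ALT above 3, the entry rule is the stricter one on bilirubin (> 1.5 against ≥ 2), as the fourth row shows. The main mismatch comes from the ALP condition.

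**Step 4: timing.** The Schedule of Activities (Section 1.3) has chemistry at Day 3 (±1 day). A child in the gap whose values have not changed meets the Section 7.1 and 8.4.7 limits at that visit.

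**Step 5: comparison with another rule.** For QTc, criterion 11 excludes above 500 msec and Section 7.1 acts above 500 msec. The two match. For the liver rules they do not, and the protocol gives no reason.

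**The case against.** The strongest case on the other side has four parts.

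- **Judgment already covers this.** Criterion 8 and Section 8.9.1 let an investigator turn such a child away, and Section 8.9.2.1 repeats chemistry on Day 1 if the screening result is more than 2 days old. This stands as mitigation. Neither clause sets a liver limit, so nothing requires the exclusion and sites may differ.
- **The two rules serve different times, and interruption is optional.** This is true, and the thresholds need not be identical. However, permanent discontinuation for persisting values is worded more firmly, and it applies whatever the cause.
- **The primary endpoint is protected.** A reader might infer that these children distort the primary safety result. The documents do not support that. The endpoint is treatment-related AEs (Section 9.4.2). Section 10.3.2 leaves out expected fluctuation in a pre-existing condition that does not worsen, and the causality guidance in Section 10.3.5 points to unrelated where another cause is more likely. An unchanged baseline abnormality need not be counted at all.
- **No planned table shows the effect.** A reader might put it at 1/30 = 3.3 percentage points on an ECI rate, taking the roughly 30 treated participants expected in Section 9.9.2. Table 8 has no ECI row, so that rate is not a planned output, and the figure is only one participant's share. Section 9.6.3 does plan change-from-baseline summaries and predefined limits of change. These help, but they are not designed to identify who met the Section 8.4.7 values before dosing.

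**Conclusion.** The inconsistency is real and confined to a definable region: ALP above 1 and below 2 x ULN, with bilirubin at least 2 x ULN and AST or ALT at least 3 x ULN, plus the boundary case at exactly 3 x ULN. A reader might infer that anyone with ALP between 1 and 2 x ULN meets the on-treatment rule. That is wrong: with ALP 1.5 x ULN and normal bilirubin and transaminases, a child meets neither rule.

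Within the region, the consequences follow from the protocol's own text: no numeric exclusion, potential drug-induced liver injury reporting from the first on-treatment chemistry, permanent discontinuation if values persist, and no replacement. The effect is on patient safety, hepatic ECI reporting and discontinuations.

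The conclusion assumes that *normal* ALP means not above ULN and that values stay unchanged from screening or Day 1 to Day 3. The documents give no frequency for this laboratory pattern, so the number of children affected cannot be stated. The point merits correction because the change is cheap and bears on who is dosed, stopped and reported.

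**What to change.** 1. **Reconcile the three passages** (Section 5.2 criterion 12, Section 7.1 and Section 8.4.7). State what *normal* ALP means, settle the difference between > 3 and ≥ 3 x ULN, and say how the on-treatment and ECI rules treat values already present at baseline. Which thresholds stay or move is for the sponsor to decide.
2. **Add a baseline flag in Section 9.6.3** for participants whose screening or Day 1 chemistry already met the Section 8.4.7 values.
3. **Present hepatic ECIs and hepatic discontinuations** with those new since baseline shown separately from those in flagged participants.

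The cost is wording in the affected sections and one table flag. No new data are needed, since the chemistry is already collected at screening or Day 1. Depending on how the sponsor reconciles the rules, a few eligibility or on-treatment decisions may change.

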# **Modified Schwartz formula**

Creatinine clearance =  $\frac{K \times (height in cm)}{(creatinine in mg/dL)}$ 

K (proportionality constant): Male child (≥2 year to <13 years): K=0.55 Male child (≥13 year to <18 years): K=0.70 Female child (≥2 year to <18 years): K=0.55

## **Other Exclusions**

- 14. Is not expected, in the opinion of the investigator, to survive for at least 1 month after the initiation of study treatment.
- 15. Is or has an immediate family member (eg, spouse, parent/legal guardian, sibling, or child) who is investigational site or Sponsor staff directly involved with this study.

See Section 10.7, Appendix 7 for country-specific exclusion criteria requirements.

# 5.3 Lifestyle Considerations

There are no diet or activity restrictions for this study.

# 5.4 Screen Failures

Screen failures are defined as participants who consent/assent to participate in the clinical study but are not subsequently entered into the study. A minimal set of screen failure information is required to ensure transparent reporting of screen failure participants to meet the Consolidated Standards of Reporting Trials (CONSORT) publishing requirements and to respond to queries from regulatory authorities. Minimal information includes demography, screen failure details, eligibility criteria, and any adverse events or serious adverse events (SAE) meeting requirements as outlined in the data entry guidelines.

# 5.5 Participant Replacement Strategy

A participant who discontinues from study treatment or withdraws from the study will not be replaced.

### **6 STUDY INTERVENTION**

Study treatment is defined as any investigational treatment(s), marketed product(s), placebo, or medical device(s) intended to be administered to a study participant according to the study protocol.

Clinical supplies (study interventions provided by the Sponsor) will be packaged to support enrollment. Clinical supplies will be affixed with a clinical label in accordance with regulatory requirements.

## 6.1 Study Intervention(s) Administered

The interventions to be used in this study are outlined in Table 3. For dosing of the PFS see Table 1.

# Table 3Study Treatments

Arm Name	Arm Type	Intervention Name	Intervention Type	Dose Formu- lation	Unit Dose Strength(s)	Dosage Level(s)	Route of Adminis- tration	Regimen/ Treatment Period	Use	IMP or NIMP/AxMP	Sourcing
Posaconazole	Experi- mental	IV	Drug	Vial	18 mg/mL	6 mg/kg Doses are not to exceed 300 mg per administration	IV Infusion	Day 1: BID Day 2 through end of IV dosing: QD	Test Product	IMP	Centrally sourced with the ability to source locally if required
Posaconazole	Experi- mental	Powder for suspension (PFS)	Drug	Powder for Suspension	30 mg/mL	Dosing based on weight-band. To be administered to participants ≤40 kg	Oral	Days 8 – 84: QD	Test Product	IMP	Centrally sourced with the ability to source locally if required
Posaconazole	Experi- mental	Tablet	Drug	Tablet	100 mg	300 mg To be administered to participants >40 kg	Oral	Days 8 – 84: QD	Test Product	IMP	Centrally sourced with the ability to source locally if required

Abbreviations: AxMP Auxiliary Medical Product, EEA=European Economic Area, IMP= Investigational medical product, NIMP=non-investigational medical product, QD= Once daily

The classification of Investigational Medicinal Product (IMP) and Non-Investigational Medicinal Product (NIMP) in this table is based on guidance issued by the European Commission and applies to countries in the European Economic Area (EEA). Country differences with respect to the definition/classification of IMP/NIMP may exist. In these circumstances, local legislation is followed.

All supplies indicated in Table 3 will be provided per the "Sourcing" column depending upon local country operational requirements. If local sourcing, every attempt should be made to source these supplies from a single lot/batch number where possible (eg, not applicable in the case where multiple lots or batches may be required due to the length of the study, etc).

Refer to Section 8.1.8 for details regarding administration of the study intervention.

# 6.2 Preparation/Handling/Storage/Accountability

## 6.2.1 Dose Preparation

The rationale for the selection of doses to be used in this study is provided in Section 4.3, Justification for Dose.

The participant's body weight at Day 1 will be used to calculate the dose of POS IV study treatment. The participant's body weight as measured within 3 days before the first day of oral POS treatment will be used to calculate all subsequent doses of oral POS: any participant whose weight is  $\leq$ 40 kg will transition to the PFS formulation; any participant whose weight is >40 kg will transition to the tablet formulation and will receive 300 mg as 3 × 100-mg tablets. For any subsequent switch from oral to IV formulation, the IV dose will be calculated based on the participant's weight before the initial switch to an oral formulation.

Instructions for preparation of the IV infusion and the PFS oral solution are found in the Pharmacy Manual. Instructions for administration of PFS will be provided to caregivers separately.

# 6.2.2 Handling, Storage, and Accountability

The investigator or designee must confirm appropriate temperature conditions have been maintained during transit for all study intervention received, and any discrepancies are reported and resolved before use of the study intervention.

Only participants enrolled in the study may receive study intervention, and only authorized site staff may supply or administer study intervention. All study interventions must be stored in a secure, environmentally controlled, and monitored (manual or automated) area in accordance with the labeled storage conditions with access limited to the investigator and authorized site staff.

The investigator, institution, or the head of the medical institution (where applicable) is responsible for study intervention accountability, reconciliation, and record maintenance (ie, receipt, reconciliation, and final disposition records).

For all study sites, the local country Sponsor personnel or designee will provide appropriate documentation that must be completed for drug accountability and return, or local discard and destruction if appropriate. Where local discard and destruction is appropriate, the investigator is responsible for ensuring that a local discard/destruction procedure is documented.

The study site is responsible for recording the lot number, manufacturer, and expiry date for any locally purchased product (if applicable) as per local guidelines unless otherwise instructed by the Sponsor.

The investigator shall take responsibility for and shall take all steps to maintain appropriate records and ensure appropriate supply, storage, handling, distribution, and usage of study interventions in accordance with the protocol and any applicable laws and regulations.

# 6.3 Measures to Minimize Bias: Randomization and Blinding

# 6.3.1 Intervention Assignment

Participants in this study will be allocated by nonrandom assignment.

All participants will receive POS as study treatment throughout the study, with the initial formulation for all participants being the IV formulation. Allocation numbers will be assigned by an IRT system.

# 6.3.2 Stratification

Treatment randomization/allocation will be stratified according to the following factors:

Participant's age at the time of first dose of study treatment:

- 1. Age Cohort 1: 2 years to <12 years of age.
- 2. Age Cohort 2: 12 years to <18 years of age.

# 6.3.3 Blinding

This study is an open-label study; therefore, the Sponsor, investigator and participant will know the treatment administered.

# 6.4 Study Intervention Compliance

The volume of injection and the number of tablets/sachets remaining in study packaging will be counted, reviewed, and recorded at regular intervals to monitor treatment compliance.

The shifting of the timing of a dose (within the window provided in Section 8.1.8 to accommodate a participant's schedule) is not considered an interruption.

Interruptions from the protocol-specified treatment plan for  $\geq$ 7 days require consultation between the investigator and the Sponsor and written documentation of the collaborative decision on participant management.

